8 SAFETY ANALYSIS

Unless otherwise specified, all available data will be listed and summary tables for safety assessments will be presented by injection route (IM or SQ), CD388 dose, and pooled placebo for the safety population as detailed in [Table 6](#).

Continuous variables will be summarized (absolute values and change from baseline) using descriptive statistics. The TEAEs occurring after the first single dose and after the second single dose will be analyzed separately.

Table 6: Data Presentations for Safety Assessment

Data	Variables	Presentation
Adverse events	Adverse event, description, date and time, severity, relationship to study drug, action taken with study drug, whether the AE caused the subject to discontinue from the study, study days, and outcome, Duration of AE, Date and time of onset, date, and time of resolution.	
Listings:
 
• Reported AEs,• Serious Adverse Event (SAE) 
Summary Tables, including number and percentage of subjects experiencing:
 
• Treatment-emergent adverse events (TEAEs),• TEAEs related to study drug• TEAEs by severity,• Serious TEAEs,• Influenza-like TEAEs (reported during the outpatient follow-up period),• Adverse Events of Special Interest (AESIs),• TEAEs leading to study withdrawal• TEAEs leading to study drug withdrawal (cohorts 2a, 2b, 3a, 3b)• Overall summary will include:
○ At Least One TEAE○ At Least One Drug-Related TEAE○ Maximum Severity:
➢ Mild,➢ Moderate➢ Severe➢ Life-threatening➢ Death○ At Least One SAE○ At Least One Drug-Related SAE○ Death○ AE leading to study drug withdrawal (Pooling placebo from cohorts 2a, 2b, 3a, 3b)○ AE leading to study withdrawal
Concomitant medications	All medications taken during the study (as defined in the protocol and including prior medications that are continued), dose, units, route, indication/ reason taken, and date and time.	
Listing
 
• Note: includes coded terms (anatomic therapeutic chemical [ATC] level 4 and preferred name)

Data	Variables	Presentation																
Extent of exposure	Study drug administration dose, Route, units, date, time, Cohort	
Listing
																
Clinical laboratory evaluations	
Laboratory results (refer to section 8.2 for parameters)
	
Listings:
 
 • All laboratory values by category, • Subjects with a potentially clinically significant (PCS) laboratory value by category 
Summary Tables:
 
 • Laboratory values and change from baseline by visit. • Number and percentage of subjects with at least one post baseline laboratory value that is deemed PCS (as defined in Table 8, Table 9, • Table 10 PCS Values for Lipids 
  
 Laboratory Parameter , Unit	PCS Range	
   
 Triglycerides, mg/dl	> 500	
 
 Low Density Lipoprotein (LDL), mg/dl	> or = 190	
 
 Cholesterol, Total, mg/dl	> = or 300	
  
 • Table 11 PCS Values for Coagulation 
  
 Laboratory Parameter , Unit	PCS Range	
   
 Activated partial thromboplastin time, seconds	> or = 1.66 x ULN	
 
 Prothrombin, International normalized ratio (INR), Ratio	> or = 1.5 x ULN	
 
 Prothrombin Time, seconds	> or = 1.25 x ULN	
  
 
Table 12 PCS Values for Urinalysis
	Laboratory Parameter , Unit	PCS Range	Triglycerides, mg/dl	> 500	Low Density Lipoprotein (LDL), mg/dl	> or = 190	Cholesterol, Total, mg/dl	> = or 300	Laboratory Parameter , Unit	PCS Range	Activated partial thromboplastin time, seconds	> or = 1.66 x ULN	Prothrombin, International normalized ratio (INR), Ratio	> or = 1.5 x ULN	Prothrombin Time, seconds	> or = 1.25 x ULN
Laboratory Parameter , Unit	PCS Range																	
Triglycerides, mg/dl	> 500																	
Low Density Lipoprotein (LDL), mg/dl	> or = 190																	
Cholesterol, Total, mg/dl	> = or 300																	
Laboratory Parameter , Unit	PCS Range																	
Activated partial thromboplastin time, seconds	> or = 1.66 x ULN																	
Prothrombin, International normalized ratio (INR), Ratio	> or = 1.5 x ULN																	
Prothrombin Time, seconds	> or = 1.25 x ULN																	

Data	Variables	Presentation	
		Laboratory Parameter	PCS Range
		Bilirubin	1+
		Erythrocyte (/HPF)	> or = 10
		Glucose	2+
		Ketones	1+
		Leukocyte Esterase	1+
		Nitrite	1+
		Occult Blood	Trace
		Protein	2+
		
 • Table 10, Table 11, Table 12) by category. • Number and percentage of subjects with a laboratory value that is deemed PCS, for each scheduled post baseline assessment time point 	
Vital signs	Blood pressure, pulse, respiration rate, and body temperature	Listings: 
 • All vital signs values, • PCS vital sign values Summary Tables: 
 • Vital signs values and change from baseline by visit and timepoint. • Number and percentage of subjects with at least one post baseline PCS value will be summarized for the worst post baseline value. • Number and percentage of subjects with a vital sign value that is PCS, for each scheduled postbaseline assessment time point 	
Physical examination	Physical examination findings	Listing: 
 • All physical examination findings 	
12-Lead Digital Electrocardiograms	ECG interpretations and findings;	Listings: 
 • All ECGs, • Clinically significant ECGs, Summary Tables 
 • ECGs parameters values and change from baseline by visit and timepoint. • Categorical QT/QTc analysis by Visit and timepoint. 	
Reactogenicity/Injection Site Inspection	Reactogenicity/Injection Site Inspection findings	Listing Table	

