
 To determine the PK profile of CD388 Injection in upper respiratory tract after IM or SQ administration as a single dose to healthy adult subjects. To identify CD388 metabolites in plasma, CD388 and its metabolites in urine, and CD388 drug-antibody ratio (DAR) distribution in plasma, and CD388 glycoforms in serum after IM or SQ administration to healthy adult subjects. To evaluate biomarkers that may be associated with AEs after CD388 Injection. To evaluate CD388 immunogenicity. To explore pharmacogenomics related to CD388. To explore the effects on cardiac safety in subjects administered CD388 Injection. To explore the effect of CD388 Injection on the occurrence of influenza-like illness (during flu season). 	
 Pharmacokinetic parameters following CD388 Injection administration: maximum nasopharyngeal (NP) concentration (C_{max}), time to maximum NP concentration (T_{max}), area under the NP concentration-time curve from time 0 to time of last quantifiable sample (AUC_{0-t}). CD388 metabolites (e.g., free zanamivir, zanamivir dimers) in plasma and urine, CD388 in urine and nasal wash, CD388 DAR distribution in plasma, and CD388 glycoforms in serum, to be reported separately. Results of the analyses of exploratory biomarkers (including but not limited to cytokines, chemokines, acute phase reactants, etc.). Anti-drug antibody titers in blood (plasma or serum). Results of the analyses of pharmacogenomic samples, to be reported separately. 12-lead ECG and Holter monitoring parameters. Influenza-like illness reporting during the outpatient follow-up period.

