Exploratory	
 To determine the PK profile of CD388 Injection in upper respiratory tract after IM or SQ administration as a single dose to healthy adult subjects. Pharmacokinetic parameters following CD388 Injection administration: maximum nasopharyngeal (NP) concentration (C_{max}), time to maximum NP concentration (T_{max}), area under the NP concentration-time curve from time 0 to time of last quantifiable sample (AUC_{0-t}). CD388 metabolites (e.g., free zanamivir, zanamivir dimers) in plasma and urine, CD388 in urine and nasal wash, CD388 DAR distribution in plasma, and CD388 glycoforms in serum, to be reported separately. Results of the analyses of exploratory biomarkers (including but not limited to cytokines, chemokines, acute phase reactants, etc.). Anti-drug antibody titers in blood (plasma or serum). To identify CD388 metabolites in plasma, CD388 and its metabolites in urine, and CD388 drug-antibody ratio (DAR) distribution in plasma, and CD388 glycoforms in serum after IM or SQ administration to healthy adult subjects. To evaluate biomarkers that may be associated with AEs after CD388 Injection. To evaluate CD388 immunogenicity.

Objectives	Endpoints

• To explore pharmacogenomics related to CD388.• To explore the effects on cardiac safety in subjects administered CD388 Injection.• To explore the effect of CD388 Injection on the occurrence of influenza-like illness (during flu season).	
• Results of the analyses of pharmacogenomic samples, to be reported separately.• 12-lead ECG and Holter monitoring parameters.• Influenza-like illness reporting during the outpatient follow-up period.

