pH	Male gender, Age to 133Y: 5.0-8.0 Female gender, Age to 133Y: 5.0-8.0
Protein	Male gender, Age to 133Y: Negative Female gender, Age to 133Y: Negative
Specific Gravity	Male gender, Age to 133Y: 1.001-1.035 Female gender, Age to 133Y: 1.001-1.035

SEROLOGY

Laboratory Parameter , Unit	Normal Reference Range
Hepatitis B surface antigen (HBsAg)	Male gender, Age to 133Y: NON-REACTIVE Female gender, Age to 133Y: NON-REACTIVE
Hepatitis C antibody	Male gender, Age to 133Y: NON-REACTIVE Female gender, Age to 133Y: NON-REACTIVE
Human immunodeficiency virus (HIV) antibody	Male gender, Age to 133Y: NON-REACTIVE Female gender, Age to 133Y: NON-REACTIVE

OTHER

Laboratory Parameter , Unit	Normal Reference Range
Opioids	Male gender, Age to 133Y: NEGATIVE Female gender, Age to 133Y: NEGATIVE
Benzodiazepines	Male gender, Age to 133Y: NEGATIVE Female gender, Age to 133Y: NEGATIVE
Barbiturates	Male gender, Age to 133Y: NEGATIVE Female gender, Age to 133Y: NEGATIVE
Cocaine metabolites	Male gender, Age to 133Y: NEGATIVE Female gender, Age to 133Y: NEGATIVE
Cannabinoids	Male gender, Age to 133Y: NEGATIVE Female gender, Age to 133Y: NEGATIVE
Methamphetamines	Male gender, Age to 133Y: NEGATIVE Female gender, Age to 133Y: NEGATIVE
Phencyclidine	Male gender, Age to 133Y: NEGATIVE Female gender, Age to 133Y: NEGATIVE

Amphetamine	Male gender, Age to 133Y: NEGATIVE Female gender, Age to 133Y: NEGATIVE
Cotinine, MCG/m:	Male gender, Age to 133Y: NEGATIVE Female gender, Age to 133Y: NEGATIVE
Alcohol	Male gender, Age to 133Y: NEGATIVE Female gender, Age to 133Y: NEGATIVE

TABLE, FIGURE, AND LISTING SHELLS

Cidara Therapeutics, Inc.

PROTOCOL No.: CD388.IM.SQ.1.01

A Phase 1, Randomized, Double-Blind, Single-Dose and Repeat Single Dose, Dose-Escalation Study to Determine the Safety, Tolerability, and Pharmacokinetics of CD388 Intramuscular or Subcutaneous Administration in Healthy Subjects

Protocol Version (Date): Amendment 2.0 (07-Feb-2023)

Altasciences Project No. CID-P1-144

Prepared by:

Altasciences Inc.
[name]
Laval, Quebec
Canada, H7V 4B3

Version: Final Amendment 3.0
Date: 2023-12-20

Version Control

Version	Date	Author	Description of Changes
1.0	2022-06-08	[name]/ [name]	Not applicable
1.1	2023-04-05	[name]/ [name]	A SAP is being updated due to the protocol amendment 2.0 (07-Feb-2023) which added a new cohort 4B for SQ route. All impacted sections are updated.

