Table 14.3.1.10: "Serious Treatment-Emergent Adverse Events (TEAEs) by System Organ Class and Preferred Term - Second Dose" i.e., Cohorts 2A, 2B, 3A, 3B, and pooled placebo of respective route will follow the same layout.

Table 14.2.18 Template T3.6: Influenza-like Treatment-Emergent Adverse Events (TEAEs) by System Organ Class and Preferred Term (Safety Population)

Table 14.3.1.13
 Influenza-like Treatment-Emergent Adverse Events (TEAEs) by System Organ Class and Preferred Term - First Dose
 (Safety Population)

MedDRA System Organ Class Preferred Term	IM Route				SQ Route				Pooled Placebo (N = XX)
	CD388 50 mg (N = XX)	CD388 150 mg (N = XX)	CD388 450 mg (N = XX)	Pooled Placebo (N = XX)	CD388 50 mg (N = XX)	CD388 150 mg (N = XX)	CD388 450 mg (N = XX)	CD388 900 mg (N = XX)	
	n (%)	n (%)	n (%)	n (%)	n (%)	n (%)	n (%)	n (%)	
Subjects with at least one TEAE	xx (xx.x)	xx (xx.x)	xx (xx.x)	xx (xx.x)	xx (xx.x)	xx (xx.x)	xx (xx.x)	xx (xx.x)	xx (xx.x)
SOC 1	xx (xx.x)	xx (xx.x)	xx (xx.x)	xx (xx.x)	xx (xx.x)	xx (xx.x)	xx (xx.x)	xx (xx.x)	xx (xx.x)
PT 1	xx (xx.x)	xx (xx.x)	xx (xx.x)	xx (xx.x)	xx (xx.x)	xx (xx.x)	xx (xx.x)	xx (xx.x)	xx (xx.x)
PT 2	xx (xx.x)	xx (xx.x)	xx (xx.x)	xx (xx.x)	xx (xx.x)	xx (xx.x)	xx (xx.x)	xx (xx.x)	xx (xx.x)
PT 3	xx (xx.x)	xx (xx.x)	xx (xx.x)	xx (xx.x)	xx (xx.x)	xx (xx.x)	xx (xx.x)	xx (xx.x)	xx (xx.x)
SOC 2	xx (xx.x)	xx (xx.x)	xx (xx.x)	xx (xx.x)	xx (xx.x)	xx (xx.x)	xx (xx.x)	xx (xx.x)	xx (xx.x)
PT 1	xx (xx.x)	xx (xx.x)	xx (xx.x)	xx (xx.x)	xx (xx.x)	xx (xx.x)	xx (xx.x)	xx (xx.x)	xx (xx.x)
PT 2	xx (xx.x)	xx (xx.x)	xx (xx.x)	xx (xx.x)	xx (xx.x)	xx (xx.x)	xx (xx.x)	xx (xx.x)	xx (xx.x)
PT 3	xx (xx.x)	xx (xx.x)	xx (xx.x)	xx (xx.x)	xx (xx.x)	xx (xx.x)	xx (xx.x)	xx (xx.x)	xx (xx.x)
...	xx (xx.x)	xx (xx.x)	xx (xx.x)	xx (xx.x)	xx (xx.x)	xx (xx.x)	xx (xx.x)	xx (xx.x)	xx (xx.x)

Date: VERSION - YYYY-MM-DD

Data Source: XXXX

Program Source: XXXXX.sas

IM = Intramuscular; SQ = Subcutaneous.

Notes:

For each row category, a subject with two or more adverse events in that category is counted only once.

Percentages are based on the number of subjects in the safety population (N).

Influenza-like TEAE are those events which were collected during Follow-up Period.

Adverse events are coded into system organ class and preferred term using MedDRA Version 24.1.

<Programming Note>

Table 14.3.1.14: "Influenza-like Treatment-Emergent Adverse Events (TEAEs) by System Organ Class and Preferred Term - Second Dose"

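### The flu-season objective has no season-restricted analysis, so the influenza-like-illness table can mix dose with season and follow-up length, in a direction the documents do not settle

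*SAP*

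**What the plan says.** The exploratory objective in Protocol Section 5, repeated in SAP Table 1, is "To explore the effect of CD388 Injection on the occurrence of influenza-like illness (during flu season". The endpoint paired with it is "Influenza-like illness reporting during the outpatient follow-up period", which has no season limit.

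SAP Section 8, Table 6 follows the endpoint: "Influenza-like TEAEs (reported during the outpatient follow-up period". The note to shell Template T3.6 (Table 14.3.1.13 for the first dose, 14.3.1.14 for the second) reads "Influenza-like TEAE are those events which were collected during Follow-up Period", and on the denominator, "Percentages are based on the number of subjects in the safety population (N". Columns are "presented by injection route (IM or SQ), CD388 dose, and pooled placebo for the safety population".

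On timing, Protocol Section 6.1 opens each dose level only after safety review of the level below. The version control of the SAP shells refers to "protocol amendment 2.0 (07-Feb-2023) which added a new cohort 4B for SQ route". Protocol Section 4.3 reports blinded safety data on 66 subjects already dosed at the 50, 150 and 450 mg levels. AE collection runs to 4 months after dosing in Cohorts 1A and 1B, and to Day 206 in Cohort 4B.

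**The concern.** The objective names a seasonal event, but the table that answers it has no calendar element. It shows one percentage per column, whether a subject's outpatient follow-up fell in winter, in summer or across both. Follow-up length also differs between cohorts, and the percentage ignores that too.

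This would matter little if each dose were compared only with placebo subjects randomized alongside it. The columns instead set each dose against placebo pooled over cohorts within route. Because cohorts were opened in sequence, dose is tied to calendar time, and most of the 900 mg comparator is not concurrent.

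This is the study's only objective about an effect on clinical illness. Readers will compare the percentages even though no test is planned. With 8 subjects on 900 mg, the shell cannot separate no events in season from no season observed.

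**Working it through.** **Cohort counts, as planned.** Each cohort has 8 CD388 and 3 placebo subjects. Total 7 × 11 = 77; CD388 7 × 8 = 56; SQ placebo 4 × 3 = 12; IM placebo 3 × 3 = 9. All agree with Protocol Table 5. Cohorts 1A to 3B hold 6 × 11 = 66, the number Section 4.3 reports as dosed. Of the 12 SQ placebo subjects, 12 − 3 = 9 are not from Cohort 4B. The documents give no planned illness rate or person-time to reproduce.

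**Outpatient time.** Inpatient stay ends on Day 30. Cohort 4B: Days 31 to 206 = 176 days. Cohorts 1A/1B: Days 31 to about 120 = 90 days. Ratio 176/90 = 1.96.

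**In-season share of Cohort 4B's 176 days.** The amendment date gives only an earliest dosing date, taken as 8 February 2023. Season definitions are assumptions for a US site.

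| Dosing date (2023) | Days 31 to 206 | Oct–Mar | Oct–Apr | Oct–May |
|---|---|---|---|---|
| 8 Feb | 10 Mar – 1 Sep 2023 | 22 (12%) | 52 (30%) | 83 (47%) |
| 15 Mar | 14 Apr – 6 Oct 2023 | 6 (3%) | 23 (13%) | 54 (31%) |
| 1 May | 31 May – 22 Nov 2023 | 53 (30%) | 53 (30%) | 54 (31%) |
| 29 May | 28 Jun – 20 Dec 2023 | 81 (46%) | 81 (46%) | 81 (46%) |
| 1 Jul | 31 Jul 2023 – 22 Jan 2024 | 114 (65%) | 114 (65%) | 114 (65%) |
| 1 Aug | 31 Aug 2023 – 22 Feb 2024 | 145 (82%) | 145 (82%) | 145 (82%) |

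Under these definitions the share is below half for dosing up to 4 June 2023, reaches 50% on 5 June and rises after that.

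**Effect on the table with no drug effect.** Assume an in-season hazard *h* of 5% per 30 days, nil off season, and 138 first-period outpatient days for Cohorts 2B and 3B (Days 31 to 168; the documents do not fix this). Risk = 1 − exp(−*h* × in-season days/30).

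- 900 mg with 23, 52 or 81 in-season days: 3.8%, 8.3% or 12.6%.
- Other cohorts wholly in season: 1B = 1 − exp(−0.15) = 13.9%; 2B/3B = 1 − exp(−0.23) = 20.5%. With 23 days for 4B, pooled SQ placebo is (3 × 13.9 + 6 × 20.5 + 3 × 3.8)/12 = 14.7%; with 52 or 81 days it is 15.8% or 16.9%.
- Other cohorts wholly off season: 3 × 3.8/12 = 0.9%; with 52 or 81 days, 2.1% or 3.2%.

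The same 3.8% on 900 mg thus sits below placebo in one case and above it in the other.

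**Length alone.** If the same hazard applied all year, 90 days would give 1 − exp(−0.15) = 13.9% and 176 days 1 − exp(−0.293) = 25.4%. This raises 900 mg relative to Cohort 1B placebo.

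**Small numbers.** P(0 of 8) is 0.95^8 = 66%, 0.90^8 = 43% and 0.80^8 = 17% at true risks of 5%, 10% and 20%.

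**The case against.** The strongest reply is that the SAP does what the protocol endpoint asks. The season limit is already lost between objective and endpoint in the protocol, so replacing the SAP row would break agreement with the endpoint. This stands, and it is why the all-follow-up row should stay and the in-season row be added.

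It can also be said that the objective is exploratory, that Protocol Section 10 states the study has no efficacy endpoints, and that Section 12 plans no hypothesis testing. One event moves the 900 mg column by 1/8 = 12.5 points, and 0/8 against 3/12 gives a Fisher p of 0.24. All true, and it limits the weight of the point. It does not make the table answer its objective.

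Onset dates are in the AE listing, and influenza-like illness is tested for COVID-19 and flu. These let a reader place and characterize individual events. They do not supply the missing denominator, because a subject with no event and no in-season time looks the same as one followed all winter.

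**Conclusion.** The mismatch is on the face of the documents: a flu-season objective, a table with no season element, and a denominator that ignores both season and duration. The 900 mg comparison with pooled placebo can therefore carry season and follow-up length along with dose. Neither the direction nor the size can be determined.

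A reader might go further and infer that Cohort 4B's follow-up lay mostly outside flu season, so that a low 900 mg rate would look like protection. The documents do not support that. They give no dosing date for any cohort, no season definition and no results. Mostly off season holds for dosing from 8 February to 4 June 2023 under the assumed seasons, and fails after that. The earlier cohorts' calendar periods are also unknown. The shells' first version is dated 8 June 2022; if Cohort 1 was dosed on 1 April 2022, for example, only 0 to 31 of its 90 outpatient days would be in season under the same definitions. Cohort 4B's longer follow-up pushes the other way.

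The percentages in the working are illustrations of how far the table could move, not estimates. The point is worth fixing because the change is cheap, but it touches one exploratory, descriptive table.

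**What to change.** Before final unblinding:

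- Define flu season by fixed calendar dates for the US site.
- In SAP Table 6 and shells 14.3.1.13/14.3.1.14, add a row for influenza-like TEAEs with onset in season during outpatient follow-up.
- Beside it, give in-season person-days and events per 100 in-season person-days by column, for the first and second dose separately. Do not use a percentage of subjects with at least one in-season day, because that counts 1 day the same as 176.
- Mark columns with no in-season time as not evaluable.
- Show Cohort 4B's three concurrent placebo subjects separately, beside pooled placebo.
- Keep the all-follow-up row, which matches the protocol endpoint.

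The cost is SAP and shell wording plus a season flag and a person-day count derived from onset, dosing and visit dates already collected. The downside is fewer events and sparser cells in an already small table.

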8.1 Adverse Events

Treatment-emergent adverse events (TEAEs) are AEs that are not present prior to the exposure to study drug or AEs that are already present that worsen in severity or frequency following exposure to study drug. All summary tables (except where noted) will present TEAEs. If a subject has more than one TEAE with the same PT (after the same dose, if applicable), it is counted once in the summary tables at the strongest relationship to study drug and at the highest severity.

All TEAEs will be coded using Medical Dictionary for Regulatory Activities (MedDRA) Version 24.1. The listing and summaries will include coded SOC and PT. Events will be listed by study drug, subject, and AE onset date. Treatment-emergent Adverse Event duration (stop date/time - start date/time), management, concomitant laboratory, vitals, and clinical examination abnormalities will be included in the listing.

8.2 Clinical Laboratory Evaluations

Laboratory data will be presented using units as reported by the clinical laboratory. Specific hematology, clinical chemistry, urinalysis, coagulation, and serology parameters are listed in [Table 7](#).

Table 7: Clinical Laboratory Evaluations

Laboratory Test Category	Specific Laboratory Tests	
Hematology:	Hemoglobin	Neutrophils (absolute)
	Hematocrit	Monocytes
	Erythrocyte (red blood count [RBC]) count	Eosinophils
	Quantitative platelet count	Lymphocytes
	Total leukocyte (white blood cell [WBC]) count	Basophils
	Mean corpuscular hemoglobin (MCH)	Mean corpuscular volume (MCV)
Serum Chemistry:	Aspartate aminotransferase (AST)	Calcium
	Alanine aminotransferase (ALT)	CO ₂ or bicarbonate
	Alkaline phosphatase (ALP)	Blood urea nitrogen (BUN) or urea
	Albumin	Creatinine
	Total bilirubin (if total bilirubin is $\geq 2 \times$ ULN with no evidence of Gilbert's syndrome, then fractionate into direct and indirect bilirubin)	Glucose
	Sodium	Chloride
	Potassium	Lipase
	Total protein	Lactate dehydrogenase (LDH)
	Phosphorus	Amylase
	Creatinine Clearance (Cockcroft-Gault)	
	Triglycerides	Low Density Lipoproteins (LDL)
Lipids:	Cholesterol, Total	
	Activated partial thromboplastin time (aPTT)	International normalized ratio for prothrombin time (INR/PT)
Complement Activation:	Complement C3, C4, CH50	

Laboratory Test Category	Specific Laboratory Tests	
Urinalysis:	pH	Occult blood
	Protein	Specific gravity
	Glucose	Ketones
	Appearance	Color
	Bilirubin	Leukocyte esterase
	Nitrite	Microscopic reflex if protein, nitrite, blood or leukocyte esterase are positive (WBC, RBC, epithelial cells, bacteria, casts, other findings)
Serology:	Hepatitis B surface antigen (HBsAg)	Human immunodeficiency virus (HIV) antibody
	Hepatitis C antibody	Severe acute respiratory syndrome coronavirus 2 (SARS-CoV-2) polymerase chain reaction (PCR)
Pregnancy	Serum beta human chorionic gonadotropin (β -hCG) pregnancy test for females of childbearing potential (screening and Day 120 only), urine or serum test at all other specified visits	Follicle-stimulating hormone (FSH), if applicable to confirm postmenopausal status, is only required once
Other	Drug (opioids, benzodiazepines, barbiturates, cocaine metabolites, cannabinoids, methamphetamines, phencyclidine, amphetamine, cotinine) and alcohol screen	

Values for continuous laboratory parameters (hematology, chemistry, urinalysis, and coagulation) will be summarized by visit and for the change from baseline using descriptive statistics. The number and percentage of subjects with at least one post baseline PCS value and value that is PCS, for each scheduled post baseline of each laboratory parameter will also be presented. Serology, alcohol/drug screen, and pregnancy test results will be presented in separate listings.

Data listings will include out-of-range flags (L, H) and whether the abnormal values are clinically significant or not and an indication of whether the value meets the PCS criterion.

PCS values for laboratory parameters (as defined in [Table 8](#), [Table 9](#), [Table 10](#), [Table 11](#), [Table 12](#) below) will be listed by category. Normal reference ranges are presented in [APPENDIX D](#).

Table 8: PCS Values for Hematology

Laboratory Parameter (Unit)	PCS Range
Absolute basophils, cells/uL	> 400
Absolute eosinophils, cells/uL	> 800
Absolute lymphocytes, cells/uL	< 600
Absolute monocytes, cells/uL	< 10, > 2100
Absolute neutrophils, cells/uL	< or = 799, > 9000
Erythrocytes, (million/uL)	Male: < 3.8, > 6.4 Female: < 3.3, > 5.5

Laboratory Parameter (Unit)	PCS Range
Hematocrit, %	<20.0,>60.0
Hemoglobin, g/dL	Male: < 10 Female: < 9.5
Leukocytes, (thousands/uL)	< 2.0. > 25.0
Platelet count, thousands/uL	< 100,> 700

Table 9: PCS Values for Serum Chemistry

Laboratory Parameter ,Unit	PCS Range
Alanine aminotransferase, U/L	>or= 1.25 x ULN
Albumin, g/dL	<3.0,>6.0
Alkaline phosphatase, U/L	>or= 2.5 x ULN
Asparate Aminotransferase, U/L	>or= 1.25 x ULN
Amylase, U/L	>or= 1.5 x ULN
Bilirubin total, mg/dL	>or= 1.1 x ULN
Blood urea nitrogen, mg/dL	> 70
Calcium, mg/dL	<7.8,>or= 12.4
Carbon dioxide, mmol/L	<16,>40
Chloride, mmol/L	<65,> 130
Creatinine, mg/dL	> or = 1.1 x ULN
Creatinine Clearance, Estimated, mL/min	< 90
Glucose, nonfasting, mg/dL	<54,>160
Lipase, U/L	> or= 1.5 x ULN
Phosphorus, mg/dL	<2
Potassium, mmol/L	<3,>or=6
Protein total, g/dL	<3.0,>9.0
Sodium, mmol/L	<130,>or=150

Table 10 PCS Values for Lipids

Laboratory Parameter , Unit	PCS Range
Triglycerides, mg/dl	> 500
Low Density Lipoprotein (LDL), mg/dl	> or = 190
Cholesterol, Total, mg/dl	> = or 300

Table 11 PCS Values for Coagulation

Laboratory Parameter , Unit	PCS Range
Activated partial thromboplastin time, seconds	> or = 1.66 x ULN
Prothrombin, International normalized ratio (INR), Ratio	> or = 1.5 x ULN
Prothrombin Time, seconds	> or = 1.25 x ULN

Table 12 PCS Values for Urinalysis

Laboratory Parameter	PCS Range
Bilirubin	1+
Erythrocyte (/HPF)	> or = 10
Glucose	2+
Ketones	1+
Leukocyte Esterase	1+
Nitrite	1+
Occult Blood	Trace
Protein	2+

